## **Specific Aim 3: Evaluate the safety of oxygen administration by measuring reactive oxygen species in maternal and cord blood**

In order to safely apply maternal oxygen administration for intrauterine fetal resuscitation, the risks of oxygen exposure must be further explored. Over-oxygenation can result in free radical formation, downstream effects of which include cell membrane and DNA damage and resultant carcinogenesis. Although oxygen supplementation is often critical to resuscitation in most settings, studies evaluating hyperoxygenation in adults and animals have shown detrimental cardiac, pulmonary, and cerebral effects. Over-oxygenation in neonates has been shown to be associated with bronchopulmonary dysplasia and retinopathy. Furthermore, reintroduction of oxygen after a period of hypooxygenation can result in adverse effects as the fetus and newborn lack robust antioxidant systems.

One of the primary markers of oxidative stress studied in the literature is malondialdehyde (MDA). The presence of reactive oxygen species results in degradation of lipids and resultant formation of MDA which then modifies endogenous proteins. MDA levels, therefore, have been studied as a surrogate for oxidative stress. (Figure 2)

[figure not shown]

Figure 2: Pathway of oxidative stress

Increased MDA levels in the neonate may be consequential and have been associated with morbidity including hyperbilirubinemia and hypoxic-ischemic encephalopathy. There is also evidence that MDA can be transplacentally transported and thus, both mother and fetus are at risk for downstream effects.

Prior studies have evaluated the relationship between maternal oxygen administration in labor and markers of free radical formation with mixed results. We hypothesize that maternal hyperoxygenation for Category II FHT is associated with increased oxidative stress in the mother and fetus. We will measure MDA in maternal and neonatal cord blood samples as a gage for oxidative stress and to assess the relationship between oxygen administration and subsequent free radical formation.

### **Significant and Potential Impact**

Current practice on our Labor and Delivery is maternal oxygen administration in the presence of Category II FHT for the duration of labor. This practice is unproven in benefit thus far and in fact, some studies suggest harm. Although it may improve fetal oxygenation, evidence thus far does not show an improvement in fetal acid-base status which ultimately correlates with neonatal outcomes. Our study has the potential to create a paradigm shift in intrauterine fetal resuscitation and has significant clinical implications for the fetus and mother. No prior clinical trials in this setting have used cord lactate as a primary outcome. Umbilical cord lactate is an established marker of asphyxia and predictor of neonatal morbidity and serves as a useful assessment of the benefit, or lack thereof, of oxygen for fetal resuscitation. Prior studies have mainly evaluated cord pH as the primary outcome which not only falls behind lactate as a predictor of neonatal outcomes, but also does not serve as an accurate reflection of the degree of metabolic acidosis that may be present due to hypooxygenation. Furthermore, previous trials addressing oxygen administration for similar indications have not employed a similar three-pronged approach to evaluating outcomes via neonatal acid-base status, FHT patterns, and free radical activity. If our stated hypothesis is proven, room air may be an equally efficacious, safer, and cost saving alternative to oxygen. Additionally, it would pave the way for further investigation into the most effective strategies for intrauterine fetal resuscitation.

## Strategy

The aim of this study is to compare maternal oxygen administration to room air for intrauterine resuscitation of Category II FHT in relation to cord gas parameters, FHT patterns, and oxidative stress in the fetus and mother. The study will be a prospective, randomized non inferiority trial to be conducted at Barnes Jewish Hospital. Current practice at our institution for intrauterine fetal resuscitation of Category II FHT include any of the combination of (1) oxygen administration via nonrebreather face mask at 10L/min (FiO2 approximately 0.80) continued for the duration of labor (2) intravenous fluid bolus (3) maternal repositioning (4) discontinuation of oxytocin. We hypothesize that room air for Category II FHT will be no different than oxygen administration in reducing the degree of fetal metabolic acidosis. This study will include term, singleton patients admitted to Labor & Delivery for spontaneous labor or labor induction. Multiples, fetal anomalies, Category III FHT, umbilical artery doppler abnormalities and preterm pregnancies will be excluded. Additionally, women will be excluded if oxygen is required for maternal indications such as hypooxygenation or cardiopulmonary disease. Our primary objective will be umbilical cord lactate. Secondary objectives include additional cord gas parameters including umbilical artery pH, umbilical artery base deficit, and umbilical vein oxygen saturation; FHT categorization and deceleration patterns; maternal and umbilical cord blood measurement of malondialdehyde.

Consent will be obtained at time of admission to Labor & Delivery. Randomization to either the oxygen group or room air group will be performed when the patient is in active labor (defined as regular contractions and  $\geq 6$  cm cervical dilation) and develops Category II FHT necessitating intrauterine resuscitation as determined by the care provider team (Figure 3). This will be performed via a computer-generated randomization sequence in a 1:1 ratio. Patients randomized to the oxygen group will receive the above stated current management of oxygen via nonrebreather face mask at 10L/min and “per-protocol” defined as receiving the mask for at least 90% of the remaining duration of labor including during cesarean delivery. Patients randomized to the room air group will not receive oxygen for Category II FHT unless otherwise required for maternal indications. Alternative and/or additional intrauterine resuscitation techniques for both groups (i.e. fluid bolus, maternal repositioning, and discontinuation of oxytocin) will be left to

the discretion of the medical team. The initial 6 patients consented and randomized will be part of a compliance run-in with the same protocol as above.

[figure not shown]

Figure 3: Flow diagram for randomization and treatment groups  
 L&D: Labor and Delivery FHT: fetal heart tracing

Specific Aim 1: Determine the effect of maternal oxygen administration for Category II FHT on neonatal cord gas parameters

After delivery of the infant, a segment of the umbilical cord will be removed with immediate collection of umbilical artery and vein samples by trained providers. These samples will be sent to the hospital laboratory for routine cord gas measurements as is universally practiced on our Labor and Delivery unit.

#### Specific Aim 2: Characterize the effect of oxygen administration on fetal heart tracing patterns

The patient's primary nurse will document the time at which intervention is initiated. A blinded investigator will then retrospectively assess FHT categorization and deceleration patterns both pre and post intervention.

Specific Aim 3: Evaluate the safety of oxygen administration by measuring ROS in maternal and neonatal blood

We will be measuring serum MDA in both cord and maternal blood as a marker of oxidative stress. MDA is a byproduct of lipid peroxidation, which occurs as a result of oxidative stress. Measurement of Thiobarbituric Acid Reactive Substances (TBARS) is a commonly used assay

for quantifying MDA This assay is performed by fluorometrically measuring the MDA-TBA complex formed in plasma or serum by the reaction of MDA and TBA.

Upon delivery of the infant, an additional sample of umbilical artery blood will be collected for this analysis. An optional sample of maternal blood will also be drawn within 60 minutes of delivery. Both blood samples will be centrifuged to collect plasma which will then be stored at -80°C until the TBARS assay is performed.

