## **Data Collection**

The patient's primary nurse will perform real-time documentation of oxygen initiation, any disruption in intervention, administration of amnioinfusion and additional resuscitation techniques performed (number of times patient is repositioned, total intravenous fluids, discontinuation of oxytocin). Study staff will collect data from medical records on:

- 1) Antepartum history:
  - a. Demographic data: Maternal age, race
  - b. Obstetric history: parity, prior cesarean, gestational age at delivery
  - c. Medical history: BMI at initial prenatal visit, diabetes, chronic hypertension, severe anemia (Hemoglobin <7), tobacco use, illicit drug use
  - d. Prenatal course: diagnosis of hypertensive disorders, gestational diabetes, abruption, intrauterine growth restriction, oligohydramnios
- 2) Intrapartum data:
  - a. Indication for admission/induction
  - b. Oxytocin (duration, total received dose)
  - c. Analgesia
  - d. Duration of labor (first and second stage)
  - e. Diagnosis of chorioamnionitis
  - f. Mode of delivery
  - g. Indication for cesarean
  - h. Electronic fetal monitoring
- 3) Neonatal course:
  - a. APGARs
  - b. Neonatal weight

- c. Admission to special care nursery (SCN) or neonatal intensive care unit (NICU)
- d. Duration of admission to SCN or NICU
- e. Diagnosis of any of the following: hypoxic ischemic encephalopathy, respiratory distress syndrome, oxygen requirement, requirement of hypothermia therapy, seizures, sepsis or suspected sepsis, neonatal death

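### The pre/post tracing review is anchored on the start of the intervention, which has no defined counterpart in the room-air arm and falls after randomization in the oxygen arm

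*Combined protocol and SAP*

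**What the plan says.** Under Strategy, Specific Aim 2, the patient's "primary nurse will document the time at which intervention is initiated". The tracing is later read against that time by a reader described as blinded, whose task is to "retrospectively assess FHT categorization and deceleration patterns both pre and post intervention". That section does not say what the start event is in each arm, and it gives no window lengths.

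Data Collection lists what the nurse records as labor proceeds: "real-time documentation of oxygen initiation, any disruption in intervention, administration of amnioinfusion", followed by other resuscitation measures (repositioning count, total fluids, stopping oxytocin). Oxygen initiation is the only start of a randomized treatment on the list. Randomization time is not on it.

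Strategy says of the comparator: "Patients randomized to the room air group will not receive oxygen for Category II FHT unless otherwise required for maternal indications". It describes no sham mask. "Alternative and/or additional intrauterine resuscitation techniques for both groups" are left to the clinical team. On timing: "Randomization to either the oxygen group or room air group will be performed when the patient is in active labor" and has developed a Category II tracing judged to need resuscitation.

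Three analyses use the anchor:
- The outcome of persistent Category II FHT after intervention (Background/Significance, Specific Aim 2), reported as an odds ratio (Statistical Analysis).
- The Kaplan-Meier fetal monitoring analyses (Statistical Analysis), for which no origin is stated.
- Subgroups 2 to 5 of the primary outcome (Statistical Analysis), defined by late, variable or prolonged decelerations or fetal tachycardia before the intervention.

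**The concern.** A before/after comparison between randomized arms needs a time zero that exists in both arms and does not depend on allocation. Mask-on meets neither condition. It happens after the allocation is known, and in the room-air arm nothing corresponds to it. The discretionary measures give no uniform substitute, because they may come at any time, repeatedly or not at all. A room-air patient who does receive oxygen, for a maternal indication or by crossover, would have an oxygen-start time unrelated to the qualifying tracing.

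Someone will therefore have to choose a room-air zero, and the plan does not say which. Randomization is the natural choice. If the oxygen arm stays on mask-on, though, a recovery in the minutes between randomization and mask-on falls before zero in one arm and after zero in the other. At stake is whether the comparison of persistent Category II FHT, which the trial hypothesizes to be no different between arms, reflects treatment or clock.

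**Working it through.** **1. The plan's own figure.** The documents give no number for the tracing time zero. The one design calculation concerns lactate (Sample size analysis): margin 0.30 × 3.5 = 1.05 mmol/L, SD 1.6, one-sided alpha 0.025, power 90%. By the normal approximation, n per arm = 2 × 1.6² × (1.960 + 1.282)² / 1.05² = 48.8, so 49 per arm and 98 in total, as stated. No tracing quantity enters, so this point leaves that figure unchanged.

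**2. The sections side by side.**

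| Item | Oxygen arm | Room-air arm |
|---|---|---|
| Anchor named in Specific Aim 2 | start of intervention | start of intervention, event not defined |
| Treatment start listed in Data Collection | oxygen initiation | none |
| Position relative to randomization | after | undefined |
| Randomization occurs | yes | yes, but not named as time zero |

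**3. Illustration of size.** Every input here is an assumption; none comes from the documents.
- There is no true effect. Time from randomization to resolution is exponential with median m = 20, 30 or 60 minutes in both arms, and resolved tracings stay resolved.
- Room air is clocked from randomization and oxygen from mask-on, d minutes later.
- Persistence is read W = 30 or 60 minutes after each arm's own zero, with all randomized patients in the denominator.

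Formulas:
- Room air: P_RA = 2^(−W/m)
- Oxygen: P_O2 = 2^(−(W+d)/m)
- Odds ratio = [P_O2/(1−P_O2)] / [P_RA/(1−P_RA)]

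Example with m = 30, W = 30, d = 10: P_RA = 2^(−1) = 0.500; P_O2 = 2^(−40/30) = 0.397; odds ratio = (0.397/0.603)/(0.500/0.500) = 0.66.

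Spurious odds ratio for persistence, oxygen versus room air:

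| m (min) | W (min) | d = 2 | d = 5 | d = 10 | d = 15 |
|---|---|---|---|---|---|
| 20 | 30 | 0.90 | 0.77 | 0.61 | 0.49 |
| 20 | 60 | 0.92 | 0.82 | 0.68 | 0.56 |
| 30 | 30 | 0.91 | 0.80 | 0.66 | 0.55 |
| 30 | 60 | 0.94 | 0.86 | 0.74 | 0.64 |
| 60 | 30 | 0.93 | 0.83 | 0.71 | 0.61 |
| 60 | 60 | 0.96 | 0.89 | 0.80 | 0.73 |

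With randomization as zero in both arms, P_O2 = P_RA and the odds ratio is 1.00 in every row.

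**4. Dependence on handling.** If oxygen patients who resolve before mask-on are dropped instead, persistence in those remaining is 2^(−(W+d)/m) / 2^(−d/m) = 2^(−W/m), and the odds ratio returns to 1.00 under this exponential model. The price is excluding patients after randomization in one arm only. The plan does not say which handling applies.

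**The case against.** The strongest reply is that Specific Aim 2 uses a neutral word, intervention, for every patient. Room air is an assigned intervention, so the nurse may be meant to note a start in both arms. Data Collection is a separate list that does not call oxygen initiation the Aim 2 anchor. Figure 3, the randomization flow diagram, could not be read in the available copy and might mark a start point. This stands in part: equating the anchor with mask-on comes from reading two sections together. It does not supply a room-air start event, and a sensible fill-in for room air still leaves the oxygen arm clocked from a later, post-randomization event.

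A reader might infer more than the documents support:

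- **That the plan prescribes different zeros by arm.** It does not. It leaves the room-air zero undefined, and the arm difference is what one plausible fill-in would produce.
- **That the blinded reader is unblinded.** A time present in only one arm could reveal allocation, but nothing says that the reader is given it.
- **That the pre-intervention subgroups are generally defined differently by arm.** Randomization follows the qualifying tracing, so that tracing precedes the intervention under either anchor. Only a pattern first appearing in the lag could be reclassified.
- **That the share resolving during the lag is the size of the error.** At an assumed 0.5 per hour, 1 − exp(−0.5 × 10/60) = 8.0% resolve in 10 minutes, and 15.4% in 20. This does not measure bias: a tracing that resolves before mask-on and stays resolved is non-persistent under either anchor.

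It is also fair to say that a common zero alone does not make the outcome reproducible, because window lengths and the Kaplan-Meier event and censoring rules are missing too.

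**Conclusion.** The concern holds as a defect in a stated analysis rule for secondary outcomes and some subgroups. The named anchor is a post-randomization event in one arm and has no defined counterpart in the other.

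The size cannot be known from the documents. Under the assumptions above it is small if the mask goes on within about 2 minutes of randomization (spurious odds ratio 0.90 to 0.96) and substantial at 10 minutes (0.61 to 0.80). In that scenario the shift favors oxygen; another room-air anchor could change the direction. It depends on persistence being read at a fixed interval after each arm's own zero.

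The analyses exposed are persistent Category II FHT, the Kaplan-Meier curves and, to a limited degree, subgroups 2 to 5. The overall intention-to-treat lactate comparison is untouched.

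**What to change.** In Strategy, Specific Aim 2, state that randomization time is time zero in both arms for the pre and post tracing windows, the Kaplan-Meier origin and the pre-intervention subgroups, and that the blinded reader receives only that time. Keep oxygen start and interruption times for reporting adherence.

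Add randomization time to the items in Data Collection. Randomization takes place in both arms, but the documents do not list its time as recorded, so it should not be taken as already available.

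The cost is one sentence and one data field, with no change to patient care or sample size. The window lengths and the Kaplan-Meier event and censoring rules are best written at the same time, as a separate addition.

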## **Data Collection**

The patient's primary nurse will perform real-time documentation of oxygen initiation, any disruption in intervention, administration of amnioinfusion and additional resuscitation techniques performed (number of times patient is repositioned, total intravenous fluids, discontinuation of oxytocin). Study staff will collect data from medical records on:

- 1) Antepartum history:
  - a. Demographic data: Maternal age, race
  - b. Obstetric history: parity, prior cesarean, gestational age at delivery
  - c. Medical history: BMI at initial prenatal visit, diabetes, chronic hypertension, severe anemia (Hemoglobin <7), tobacco use, illicit drug use
  - d. Prenatal course: diagnosis of hypertensive disorders, gestational diabetes, abruption, intrauterine growth restriction, oligohydramnios
- 2) Intrapartum data:
  - a. Indication for admission/induction
  - b. Oxytocin (duration, total received dose)
  - c. Analgesia
  - d. Duration of labor (first and second stage)
  - e. Diagnosis of chorioamnionitis
  - f. Mode of delivery
  - g. Indication for cesarean
  - h. Electronic fetal monitoring
- 3) Neonatal course:
  - a. APGARs
  - b. Neonatal weight

- c. Admission to special care nursery (SCN) or neonatal intensive care unit (NICU)
- d. Duration of admission to SCN or NICU
- e. Diagnosis of any of the following: hypoxic ischemic encephalopathy, respiratory distress syndrome, oxygen requirement, requirement of hypothermia therapy, seizures, sepsis or suspected sepsis, neonatal death

## **Data and Safety Monitoring Plan**

In addition to principle investigator review of adverse events, a data and safety monitoring board (DSMB) will be established. This board will have three individuals ([name], [name], [name]) not directly involved in the study. The DSMB will meet once 50% of participants have been recruited to review any adverse neonatal or maternal events among the study cohort and determining safety of continuing the study to completion. The DSMB will receive a report of any severe and/or non-severe adverse neonatal outcomes within 72 hours of occurrence. Reportable severe adverse neonatal outcomes include intrapartum stillbirth and neonatal death. Reportable non-severe adverse neonatal outcomes include need for hypothermia protocol, seizures, and prolonged NICU stay >72 hours.

## **Statistical Analysis**

Intention-to-treat (primary analysis) and per protocol analyses will be performed. Chi-squared and Fisher's exact tests will be used to compare categorical variables as appropriate. Continuous variables will initially be assessed for distribution pattern via the Kolmogorov-Smirnov test. Normally distributed variables will be compared using Student's t-tests and non-normally distributed variables will be analyzed with the Mann-Whitney U test. These analyses will be supplemented by multivariable logistic regressions to adjust for confounders.

Tests with  $p < 0.05$  will be considered statistically significant. Analyses will be performed using Stata (Stata Corp., College Station, TX).

For the primary outcome of lactate, 95% confidence intervals (CI) will be calculated for the mean cord lactate levels in each group. Comparison of the 95% CI in each group will then determine non-inferiority or inferiority.

Additional interaction analyses for the primary outcome will be performed for the following subgroups:

- 1) Presence of chronic medical conditions (hypertensive disorder, diabetes)

- a. Patients with hypertensive disorders (chronic hypertension, gestational hypertension, preeclampsia)
- b. Patients with diabetes mellitus (gestational diabetes, T1DM, T2DM)
- 2) Recurrent late decelerations pre intervention
- 3) Recurrent variable decelerations pre intervention
- 4) Prolonged deceleration pre intervention
- 5) Fetal tachycardia pre intervention
- 6) Fetuses with intrauterine growth restriction
- 7) Chorioamnionitis
- 8) Within oxygen group: Duration of oxygen exposure
  - a. <50% of total duration of active labor (onset of active labor to delivery)
  - b. >50% of total duration of active labor (onset of active labor to delivery)

Odds ratios and 95% CI will be calculated for the secondary outcome of persistent Category II FHT. Kaplan-Meir analyses will be performed for fetal monitoring analyses.

For the outcome of maternal and cord blood MDA, a fetal MDA will be calculated by subtracting umbilical artery MDA from maternal MDA for each sample. The calculated mean fetal MDA and maternal MDA values will then be compared between groups using either Student t test or Mann Whitney U test.

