### **Sample size analysis**

A review of previously collected data from our institution of 5182 term singleton pregnancies revealed a mean cord lactate of  $3.5 \pm 1.6$  mmol/L in women with Category II FHT within 30 minutes of delivery. All of these deliveries were managed using our current protocol of routine oxygen administration for Category II FHT. Given the normal mean lactate seen in our population of patients with Category II FHT, a noninferiority approach was selected to test our hypothesis that room air is not inferior to oxygen administration in treating Category II FHT. A total sample size of 98 patients will be needed to detect a non-inferiority margin of 30% with 90% power, using a one-sided two-sample t-test (alpha 0.025). To accommodate a 15% drop out/cross over rate, a total of 114 patients will be needed. We plan on performing an initial compliance run-in of 6 patients making the total enrollment 120 patients. Data analysis will only be performed on the 114 patients enrolled after the initial 6 patients enrolled/randomized in the compliance run-in/pilot. Previous studies have shown an increased risk for neonatal morbidity with cord lactate cut-offs ranging from 3.2-6.0. The margin of noninferiority was

therefore set at a lactate cut-off of 4.5, above which there is a clear association with neonatal morbidity.

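### Does the lack of a stated rule for reading the per-protocol result against intention-to-treat undermine the non-inferiority claim?

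*Combined protocol and SAP*

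**What the plan says.** Statistical Analysis sets out the two analyses in one sentence: "Intention-to-treat (primary analysis) and per protocol analyses will be performed". For the primary outcome it then says: "Comparison of the 95% CI in each group will then determine non-inferiority or inferiority". That sentence names no analysis set.

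Sample size analysis derives 98 patients and adds an allowance: "To accommodate a 15% drop out/cross over rate, a total of 114 patients will be needed". The 15% is one pooled figure, not split by type of departure or by arm.

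Strategy gives a per-protocol criterion for the oxygen arm, "defined as receiving the mask for at least 90% of the remaining duration of labor including during cesarean delivery". The room-air arm has a treatment rule but no per-protocol criterion under that name: "Patients randomized to the room air group will not receive oxygen for Category II FHT unless otherwise required for maternal indications". The same section says that "women will be excluded if oxygen is required for maternal indications such as hypooxygenation or cardiopulmonary disease".

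Two further provisions bear on adherence. A six-patient compliance run-in is kept out of the analysis (Strategy; Sample size analysis). Nurses also keep "real-time documentation of oxygen initiation, any disruption in intervention" (Data Collection).

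**The concern.** A non-inferiority test rewards anything that makes the arms look alike. If oxygen works and some room-air patients receive it, the ITT difference shrinks and a false claim becomes easier. That direction of cross-over is plausible here, because routine care on this unit is oxygen: "Current practice on our Labor and Delivery is maternal oxygen administration in the presence of Category II FHT for the duration of labor". Raising the sample size protects power but does not offset the dilution. With two analyses planned and no rule linking them, it could seem that a conflicting per-protocol result might be set aside, or relied on, after the data are seen. At stake is a non-inferiority conclusion that the sponsor hopes will change routine labor care.

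**Working it through.** **Inputs.** Mean lactate 3.5 and SD 1.6 mmol/L, margin 30%, one-sided alpha 0.025, power 90%, N = 98 raised to 114 (all Sample size analysis); 1:1 allocation (Strategy). The margin is 0.30 × 3.5 = 1.05 mmol/L.

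**The plan's own figures.** With 49 per arm, SE = 1.6 × √(2/49) = 0.323. Power at zero true difference is Φ(1.05/0.323 − 1.96) = 90.1%, so 98 reproduces. For the allowance, 98/0.85 = 115.3 and 98 × 1.15 = 112.7, so 114 lies within two patients of either method. Also 114 × 0.85 = 96.9, so the inflated N leaves about the 98 required once 15% are removed. It therefore nearly preserves power for a per-protocol set: simulated per-protocol power with 15% excluded at random from each arm is 89.1%.

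**Dilution under ITT.** The true difference between receiving room air and receiving oxygen is set at the margin, d = 1.05. A share c of the room-air arm gets oxygen and a fraction k of its effect. The test is taken as the upper 95% limit of the between-arm difference lying below 1.05. This is an assumption, because the plan does not state that form. With 57 per arm, SE = 1.6 × √(2/57) = 0.2997, and

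P(claim) = Φ(c × k × 1.05/0.2997 − 1.96).

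| c | k = 1 | k = 0.5 |
|---|---|---|
| 0 | 2.5% | 2.5% |
| 5% | 3.7% | 3.1% |
| 10% | 5.4% | 3.7% |
| 15% | 7.6% | 4.5% |

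Simulation with t-tests at k = 1 gives 3.7%, 5.3% and 7.4%. At 49 per arm the formula gives 3.6%, 5.1% and 7.0%, so a larger N slightly raises this rate.

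**What these rates refer to.** They are errors about the effect of oxygen actually received. If the target is the difference between the two policies as randomised, the value tested is the diluted difference itself. When that equals the margin the rate is Φ(−1.96) = 2.5%, whatever the cross-over. If oxygen is neutral, cross-over dilutes nothing.

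**What a both-sets rule would buy.** Simulated at d = 1.05, c = 15%, k = 1, by correlation between the tendency to cross over and untreated lactate:

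| Correlation | ITT alone | Both sets |
|---|---|---|
| 0 | 7.4% | 2.4% |
| 0.2 | 7.6% | 4.3% |
| 0.4 | 7.6% | 6.2% |
| 0.6 | 7.7% | 7.5% |

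At zero true difference with 15% excluded at random per arm, power at 57 per arm is 93.5% for ITT and 88.2% for both sets. Restoring 90% needs 61 per arm, that is 122 − 114 = 8 more patients.

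**An all-randomised alternative.** Comparing the ITT upper limit with the margin × (1 − observed c) holds the error at 2.3% to 2.9% over the same correlations. It assumes one oxygen effect for all patients, and at zero difference it passes only about 91%, 88% and 84% of the time at 5%, 10% and 15% cross-over.

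**The case for a change.** The strongest case for a change is that the silence is real and concerns a departure the plan itself expects. The stated hypothesis treats room air as a replacement for oxygen, which can be read as a question about oxygen received rather than oxygen assigned. On that reading the 3.7% to 7.6% is the relevant error, the larger N does not reduce it, and a sponsor who plans a per-protocol analysis should say what it is for. A room-air criterion would also cost only a sentence.

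Part of this stands. No section gives a rule for disagreement, and the arithmetic is right on its assumptions. But nothing in the documents names the effect of oxygen received as the target, and the word primary is attached to ITT alone. The larger N is not the only response to cross-over: a per-protocol analysis, a compliance run-in and nurse documentation are all planned. The 7.6% needs the whole pooled allowance to be room-air patients crossing over with full benefit, although the allowance also covers drop-out, which does not dilute in this way. The room-air criterion follows from the treatment rule in Strategy, and the exclusion of women who need oxygen for maternal reasons should leave few doubtful cases.

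**Conclusion.** No change is called for. Followed as written, ITT decides and per-protocol is supportive. That is a valid as-randomised comparison at its nominal 2.5%. The unstated role of the per-protocol result and the unwritten room-air criterion are missing detail. An analyst would fill them by reporting both sets, showing any disagreement openly, and treating room-air patients given oxygen for Category II tracings as off protocol.

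The possible inflation, to between 3.7% and 7.6% with full effect or 3.1% and 4.5% with half effect, depends on three assumptions together: oxygen received is the target, oxygen lowers lactate by the full margin, and 5% to 15% of the room-air arm crosses over. Requiring both sets would cost about five points of power against ITT alone (93.5% to 88.2%) or eight more patients. It helps least where cross-over is most closely tied to lactate. Statisticians could reasonably choose either way.

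This conclusion does not cover how the two group intervals are to be compared, which is a separate matter. If overlap of the intervals were the rule, the false-claim rate at the margin would be about 25% with no cross-over at all.
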